CPAP has established efficacy in improving cognition. A meta-review involving review articles meeting pre-determined strict criteria, concluded that CPAP use improved executive function, long-term verbal and visual memory, attention/vigilance and global cognitive functioning [22]. Another meta-analysis also found that individuals with OSA demonstrated medium to very large impairments executive dysfunction, independent of age and disease severity, which showed small to moderate improvements following CPAP treatment [23]. In the context of Alzheimer's disease, Ancoli-Israel et al. conducted a randomized double-blind placebo-controlled trial to determine whether CPAP use resulted in improvements in neuropsychological test scores. Although the study was underpowered to make definitive conclusions about improvements within specific cognitive constructs, exploratory post hoc examination of score changes suggested that CPAP use by individuals with OSA yielded some benefits; these included improvements in episodic verbal learning and memory and some aspects of executive functioning such as cognitive flexibility and mental processing speed [24].

Although CPAP has been associated with improvements in cognitive functioning in the general population, its effectiveness in improving cognition in HIV+ individuals has never been previously tested. Given that the cognitive disturbances in this population are multi-factorial, determining whether treatment of OSA in this population improves cognition is key in improving the clinical management of HIV+ individuals, both for its negative impact on cognition but also more generally for their health.

Obstructive sleep apnea in the cohort “Understanding and Optimizing Brain Health Now”. Cohort participants (N=840) are studied prospectively over a 27-month period with visits every 9 months. Patients complete a computer-based evaluation of cognitive ability, the B-CAM, as well as questionnaires on socio-demographic characteristics, symptom status, functional status, health perception and quality of life. Given the high prevalence of OSA reported in the population, participants complete questions that, combined with other values already documented, support the scoring of two screening questionnaires for OSA, the Berlin [25, 26] and the STOP-BANG [27, 28] (see

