### **STUDY OBJECTIVES**

The overall aim is to contribute evidence about the impact of treatment of sleep apnea (with CPAP) on cognitive ability in HIV+ individuals.

The primary objective is to estimate among people with HIV and obstructive sleep apnea, the extent to which 4-7 months of CPAP impacts on cognitive ability (B-CAM), in comparison to individuals who screen positive for OSA but are not participating in the sleep apnea intervention.

An exploratory objective is to identify whether the changes are similar on measured cognitive ability and on self-reported cognitive symptoms.

The explanatory objective is to relate degree of adherence to CPAP to change in cognitive outcomes.

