### **Screening:**

Brain Health Now study participants who screen positive for the presence of OSA, meet inclusion/exclusion criteria based on the information already available as part of the main study questionnaires and who, on initial enrolment, have agreed to be contacted for sub-studies, will be approached for participation. Those who agree to participate and provide informed consent will be referred for a polysomnography (sleep study). Those with confirmed OSA will continue to the intervention phase.

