## **Effect of Continuous Positive Airway Pressure (CPAP) treatment on cognitive ability in HIV+ individuals with obstructive sleep apnea (OSA): A pilot study**

The values to be used will be those collected during the scheduled platform evaluations which occur 9-12 months apart.

- (ii) Self-reported cognitive symptoms will be measured using the C3Q (Communicating Cognitive Concerns in HIV) collected during the scheduled platform evaluations which occur 9-12 months apart.
- (iii) Adherence to the CPAP home treatment will be obtained from the CPAP device directly through its telemonitoring function, which is done by activating modems on CPAP machines and having the data transferred onto the Compliance Management Solutions. The granularity of the data will yield a continuous metric of sleep-minutes of use. Reasons for poor adherence and tolerance will be obtained by telephone contact or at clinical visits with the sleep specialist.
- (iv) Three cohorts will be compared: (i) the intervention cohort comprising all those approached who agreed to enter; (ii) the refuser cohort comprising all those approached who declined entry; and (iii) control cohort comprising eligible persons who were not approached, and hence were not given the opportunity to accept or decline.

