## **Effect of Continuous Positive Airway Pressure (CPAP) treatment on cognitive ability in HIV+ individuals with obstructive sleep apnea (OSA): A pilot study**

CAM score and C3Q. The analysis will focus on estimating the proportion of responders. A sample size of 30 participants will provide sufficient power for within-group analysis. With the assumption that the outcome is drawn from a binomial distribution with an expected probability of response of 10% (N=3) with no intervention, 30 subjects in the intervention group will allow detection of a positive response, with 80% power and  $p<0.05$ , if 7 or more persons respond (stattrek.com binomial calculator.) The proportion of responders on the different cognitive outcomes will also be estimated.

A secondary analysis will relate adherence to CPAP to change in cognitive outcomes using linear regression adjusting for age, sex, weight, baseline sleep satisfaction.

For between-cohort comparisons of cognitive outcomes, generalized estimating equations (GEE) will be used to permit both the baseline and post-intervention measures to be included along with the within-person correlation. A linear GEE will be used as the outcomes are continuous although a binary response was used for the primary objective. The model will include the indicator variable for cohort (CPAP, refuser, or control), time (assessment 1, 2), as well as confounding variables of age, sex, education, BMI, and comorbidity. As the control cohort will be very much larger than the intervention cohort, statistical comparisons have sufficient power to detect effect sizes of 0.5 or greater, suitable for a pilot study. The parameter estimated from GEE is equivalent to an adjusted effect size (adjusted between cohort effect divided by correlation adjusted standard error).

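### The between-cohort GEE adjusts for no measure of OSA likelihood or severity, although a screening score can be computed for all three cohorts

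*Protocol*

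**What the plan says.** **Model.** Statistical Analysis and Sample lists the terms of the between-cohort GEE. It begins "The model will include the indicator variable for cohort (CPAP, refuser, or control), time (assessment 1, 2" and adds "confounding variables of age, sex, education, BMI, and comorbidity". No sleep or OSA variable is named. In the same section, the adherence analysis is a "linear regression adjusting for age, sex, weight, baseline sleep satisfaction".

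**OSA status.** Under Screening, people who consent are sent for polysomnography, and "Those with confirmed OSA will continue to the intervention phase". The comparator in Study Objectives is "individuals who screen positive for OSA but are not participating in the sleep apnea intervention". Measurement describes controls as eligible people who were never approached, so no sleep study is planned for them. None is described for refusers either, and Participant Confidentiality speaks only of their positive screen.

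**Available data.** Background says that the cohort questionnaire, together with values already recorded, will "support the scoring of two screening questionnaires for OSA". The questions are in Appendix 1.

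**The concern.** A covariate belongs in a non-randomised comparison when it may differ between the groups and may be related to the outcome. OSA likelihood plausibly meets both conditions. The people on CPAP have passed a confirmatory test that the comparison groups have not taken, and Background treats OSA as a contributor to cognitive disturbance. The plan holds a screening measure for everyone compared, since eligibility depends on it, but does not use it in the model.

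At stake is the contrast that answers the primary objective. If controls include people without OSA, their untreated course may differ from the one the CPAP group would have had, and that difference would be credited to, or subtracted from, the effect of CPAP.

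**Working it through.** **1. The texts side by side**

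| Group | How OSA status is known | Screening score obtainable? |
|---|---|---|
| CPAP recipients | Positive screen, then sleep study (Screening) | Yes |
| Refusers | Positive screen only | Yes |
| Controls | Positive screen only (Study Objectives, Measurement) | Yes |

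The GEE list contains age, sex and BMI, which are related to OSA risk. It contains none of the snoring, observed-apnoea or tiredness items of Appendix 1. Background also says that traditional indicators may be less informative in people with HIV, so age, sex and BMI cannot be relied on to stand in for OSA.

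**2. The plan's own figure**

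No figure is attached to the covariate choice. The section says only that effect sizes of 0.5 or more are detectable, without a control sample size or a pre-post correlation, so that statement can be neither reproduced nor refuted. I use 0.5 below as a yardstick and read it in SD units.

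**3. Illustration of the total bias (inputs assumed)**

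Let *s* be the share of controls who truly have OSA, and *d* the amount by which untreated OSA shifts change between the two assessments, in SD. If all CPAP recipients have OSA, their untreated change would be shifted by *d* and that of controls by *s* × *d*. The bias has size (1 − *s*) × *d*.

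| | *d* = 0.1 | *d* = 0.3 |
|---|---|---|
| *s* = 0.8 | 0.2 × 0.1 = 0.02 | 0.2 × 0.3 = 0.06 |
| *s* = 0.5 | 0.5 × 0.1 = 0.05 | 0.5 × 0.3 = 0.15 |

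Against 0.5 this is 0.02/0.5 = 4% to 0.15/0.5 = 30%.

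A second illustration assumes that OSA severity differs between cohorts by 0.25 to 1.0 SD and correlates 0.1 to 0.3 with B-CAM change. The bias is the product: 0.25 × 0.1 = 0.025 to 1.0 × 0.3 = 0.30 SD.

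**4. Scale against sampling error**

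With 30 CPAP users and an assumed 100 to 470 controls, the cross-sectional standard error in SD units is √(1/30 + 1/100) = 0.21 to √(1/30 + 1/470) = 0.19. For a change contrast with an assumed pre-post correlation of 0.6, multiply by √(2 × 0.4) = 0.89, which gives 0.19 to 0.17. The largest value in the first illustration, 0.15, is below one standard error.

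**5. How the covariate must enter**

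I take the quantity of interest to be the difference between cohorts in change. With both assessments complete, a baseline covariate entered only as a main effect shifts both assessments equally and leaves that difference unadjusted. It needs an interaction with time.

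**The case against.** Most of the case on the other side stands as a limit on what may be concluded.

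- **Sleep satisfaction.** A reader might infer from the adherence regression that sleep satisfaction is cohort-wide data and was dropped inconsistently. The Protocol does not support this. The variable is absent from the cohort description in Background, from Measurement and from Appendix 1, and the adherence model asks a different question, among CPAP users only.
- **Every contrast affected.** A reader might infer that the bias arises however the cohorts are compared. It does not. Study Design says that those offered the intervention are randomly selected, so comparing everyone selected with those not approached balances OSA in expectation. Measurement also defines the intervention group as "the intervention cohort comprising all those approached who agreed to enter". Agreement comes before the sleep study, so that definition includes people whose study is negative, and the confirmation gap narrows. But the GEE enters CPAP, refuser and control as separate cohorts, and the gap is clear for those actually treated.
- **Direction.** A reader might infer that the omission hides part of CPAP's benefit. Background reports lower cognitive performance in people with OSA, not faster decline when untreated. A stable difference in level cancels in a change contrast. Both *d* and its sign are assumptions.
- **Reach of the remedy.** Everyone compared already screens positive, and the score overlaps with age, sex and BMI. No document gives its predictive value here. Eligibility by either instrument leaves some spread on each score, but no covariate can turn an unconfirmed control into a confirmed one.

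The omission itself is not answered. The Protocol fixes a covariate list, an OSA measure is available for all three cohorts, and the list leaves it out without a reason.

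**Conclusion.** The point holds in a narrow form: the covariate list omits the one OSA measure that the documents show to be obtainable in all three cohorts, although CPAP recipients are sleep-study confirmed and the others are only screen-positive. It is a cheap improvement and does not invalidate the analysis.

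The size and direction of the bias cannot be derived from the documents. The range of 0.02–0.15 SD rests on an assumed 50–80% of controls with true OSA and an assumed shift of 0.1–0.3 SD. It describes the whole bias under those assumptions, and should not be read as the amount that adjustment would recover. Adjustment removes only the part that the score predicts, and that part is unknown.

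**What to change.** In Statistical Analysis and Sample, add the OSA screening score at assessment 1 to the GEE covariates. Name one version in advance, for example the STOP-BANG item count, and state how it is scored, since Appendix 1 gives questions without scoring rules. Enter it with a time interaction so that it adjusts change.

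Add baseline sleep satisfaction only if it proves to be recorded for all three cohorts.

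State as a limitation that the adjustment covers only the imbalance the score predicts, and that OSA in controls and refusers remains unconfirmed.

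The cost is one covariate and its interaction, from data already used for eligibility. Precision may fall slightly because the score overlaps with age, sex and BMI.

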### **STUDY DESIGN**

This study is part of a larger project based upon a cohort multiple randomized controlled design [29]. Within a fully characterized cohort (N=840) which is followed over time, people meeting the specific criteria for one or more interventions (here CPAP) are identified and a sample is randomly selected to receive the intervention; the remaining eligible persons who do not receive the intervention serve as controls. This design, when operationalized for one intervention, yields three cohorts: (i) the intervention cohort comprising all those approached who agreed to enter; (ii) the refuser cohort comprising all those approached who declined entry; and (iii) control cohort comprising eligible persons who were not approached, and hence were not given the opportunity to accept or decline. For the CPAP intervention, the duration of the study is 4-7 months.

Eligible patients will be identified among the Montreal participants (N=500) in the “Understanding and Optimizing Brain Health Now” cohort study who have screened positive for the possible presence of sleep apnea on either the Berlin or the STOP-BANG and experience some cognitive difficulties as measured by the B-CAM ( $\leq 29$ ). We will continue recruitment until 30 participants have used the CPAP device for a minimum of 4 months, on at least 30% of the nights with a median of  $\geq 4$  hours/night.

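### The power claim for effect sizes of 0.5 in the between-cohort comparison does not follow from a large control cohort, and the GEE as listed has no term that isolates the change due to CPAP

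*Protocol*

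**What the plan says.** The last paragraph of Statistical Analysis and Sample compares the cohorts with a linear GEE in which baseline and post-intervention scores are both outcomes. On its terms it says "The model will include the indicator variable for cohort (CPAP, refuser, or control), time (assessment 1, 2"), followed by age, sex, education, BMI and comorbidity. No cohort-by-time term is listed, and baseline B-CAM is not among the covariates.

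The power statement follows: "statistical comparisons have sufficient power to detect effect sizes of 0.5 or greater". The only ground offered for it is the relative size of the groups: "As the control cohort will be very much larger than the intervention cohort". The protocol adds that this suits a pilot. No power level, alpha, sidedness, control count or correlation is attached. The protocol's one numerical power figure belongs to the binomial responder test in the same section, where 30 subjects "will allow detection of a positive response, with 80% power and" p<0.05.

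On cohort sizes, Study Design says "We will continue recruitment until 30 participants have used the CPAP device for a minimum of 4 months" at a set level of use. The comparison itself uses "the intervention cohort comprising all those approached who agreed to enter". The source pool is bounded: "Eligible patients will be identified among the Montreal participants (N=500"), before the OSA-screen and B-CAM criteria are applied. A third group is "the refuser cohort comprising all those approached who declined entry", with no expected size.

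**The concern.** The variance of a difference between two groups contains one term for each group. Enlarging the control cohort removes only its own term; the term for about 30 CPAP participants remains. A claim resting on control numbers alone therefore needs checking.

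The second issue is what the model estimates. When both assessments are outcomes and cohort enters only as a main effect, the cohort coefficient is the average difference over the two assessments, one of which precedes treatment. The treatment effect lies in how the cohorts differ in change, and no listed term carries that.

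Study Objectives makes the comparison with untreated screen-positive people the primary objective. If the listed model were run and its cohort coefficient reported, a real 0.5 SD effect would appear at half its size and would be missed more often than found.

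**Working it through.** **Inputs from the protocol.** Effect 0.5; 30 CPAP participants; at most 500 − 30 = 470 controls; listed terms cohort, time and confounders.

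**Assumptions.** Two-sided 5%; 80% as the benchmark, borrowed from the within-group test; outcome SD 1 at each assessment; similar baselines; r = within-person correlation, varied; control numbers varied. I read 0.5 as SD units. The protocol instead describes its effect size as an effect divided by a standard error, which is a test statistic; an expected z of 0.5 would have about 8% power, so that reading cannot be meant.

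**The plan's own figure.** It cannot be reproduced, because no inputs are attached to it. The checks below show what it would take.

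**Formula.** Power = Φ(d/SE − 1.96), SE = √[V(1/30 + 1/n)], with n controls.

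*1. Plain comparison* (d = 0.5, V = 1).

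| Controls | SE | d/SE | Power |
|---|---|---|---|
| 60 | 0.224 | 2.24 | 61% |
| 150 | 0.200 | 2.50 | 71% |
| 470 | 0.188 | 2.66 | 76% |
| unlimited | 0.183 | 2.74 | 78% |

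Even with unlimited controls, 80% needs (2.80/0.5)² ≈ 31.4, that is 32 CPAP participants.

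*2. Cohort coefficient of the listed model.* It averages 0 at baseline and 0.5 at follow-up, so d = 0.25. The mean of two correlated scores has V = (1 + r)/2.

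| r | 100 controls | 150 controls | unlimited |
|---|---|---|---|
| 0 | 40% | 42% | 49% |
| 0.4 | 30% | 32% | 37% |
| 0.5 | 28% | 30% | 35% |
| 0.7 | 26% | 27% | 32% |
| 0.8 | 24% | 26% | 30% |

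Example: r = 0.5, n = 150 gives SE = √(0.75 × 0.04) = 0.173, 0.25/0.173 = 1.44, power Φ(−0.52) = 30%. A GEE simulation with 150 controls (500 runs per cell) gave a mean coefficient of about 0.25-0.27 and power of 30% at r = 0.5 and 34% at r = 0.7.

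*3. Contrasts that do target the effect* (d = 0.5, 150 controls). Cohort-by-time change contrast: V = 2(1 − r). Baseline-adjusted contrast: V = 1 − r².

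| r | Change contrast | Baseline-adjusted |
|---|---|---|
| 0.5 | 71% | 82% |
| 0.6 | 80% | 88% |
| 0.7 | 90% | 94% |

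For the change contrast, 80% needs r of at least 0.68 with 60 controls, 0.60 with 150, 0.55 with 470 and 0.52 with unlimited controls. For the baseline-adjusted contrast the thresholds are 0.60, 0.45, 0.32 and 0.21.

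*4. Detectable effect at 80% power* (change contrast, 30 and 150). 2.80 × √[2(1 − r) × 0.04] = 0.56, 0.50 and 0.43 SD at r = 0.5, 0.6 and 0.7.

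*5. Refusers.* If there were 30 (assumed), the change contrast would have 49% power at r = 0.5 and 71% at r = 0.7.

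**The case against.** Several points on the other side are sound.

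- **No stated calculation is wrong.** The protocol says only that power is sufficient, for a pilot; 80% is borrowed from another test. This stands: the claim is unsupported rather than a miscalculation.
- **The list of terms may be incomplete.** An interaction may be intended and specified elsewhere. This stands as a condition: the halved effect and the 24-32% then fall away and only the point about the control cohort remains. The protocol does, however, attach a power claim to the model it lists, so the term belongs there.
- **Covariates may help.** If they explained 40% of the variance, the listed coefficient would reach 46-56% with 150 controls (r = 0.5-0.7). That is better, but still short of 80%.
- **The intervention cohort can exceed 30,** since it includes everyone who agreed. With 40 and 150 controls the change contrast has 80% at r = 0.5. This stands, although non-adherent entrants or those without confirmed OSA could dilute the effect, and the listed coefficient would still have only 33% at r = 0.7.
- **A one-sided test** would give 80% in the plain comparison with 150 controls. None is stated.

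A reader might infer that the study cannot detect 0.5 SD. The documents do not support that: a suitable contrast reaches 80% under ordinary conditions. A reader might also take 37% as the ceiling for the listed model. That holds only for r of 0.4 or more without covariate gain; at r = 0 it is 49%. Nor does the protocol say that the 0.5 claim will size the later study, only that the pilot's findings will inform it.

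**Conclusion.** The concern holds in two parts.

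First, a large control cohort does not by itself give adequate power for 0.5 SD. With 30 CPAP participants the plain two-sided comparison stops at 78%, and at 76% with the most controls that the Montreal pool allows. Whether 80% is reached depends on the correlation, the control count, the choice of contrast and the final size of the intervention cohort, none of which the protocol fixes.

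Second, and only if the listed terms are the whole model, the cohort coefficient targets about 0.25 SD when the follow-up effect is 0.5 SD, and the comparison serving the primary objective has roughly one chance in four to one in three of detecting it, before any gain from covariates.

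The 80% benchmark, two-sided testing, similar baselines, 100-150 controls and the values of r are assumptions. The claim is unsupported and conditional, not shown to be unattainable. It should be corrected, because the primary objective rests on this comparison.

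**What to change.** - Add the cohort-by-time term, or specify a baseline-adjusted contrast, and name it as the tested parameter for CPAP versus control.
- Replace the power sentence with a conditional one that uses the expected cohort sizes and the cohort's own B-CAM correlation between assessments. For example: assuming 30 CPAP participants and 150 controls, two-sided 5%, the change contrast has 80% power for 0.56, 0.50 or 0.43 SD at r = 0.5, 0.6 or 0.7. The detectable effect is smaller with baseline adjustment, or if the cohort of all who agreed exceeds 30. The 150 and the three correlations are placeholders for the sponsor's own figures.
- State the effect size in SD units, since an effect divided by its standard error is not a standardised effect.
- Limit the power claim to CPAP versus control, because the refuser cohort has no stated size.

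This needs no added patients and no new data collection. The downside is that the stated detectable effect may become slightly less favourable than 0.5.

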### **Measurement**

Four types of measures are under study: (i) cognitive ability; (ii) self-reported cognitive symptoms; (iii) adherence to the CPAP treatment; and (iv) cohort.

- (i) Cognitive ability will be measured using the B-CAM which comprises computerized cognitive tests and yields a score on a continuous metric [30].

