### **Statistical Analysis and Sample**

Basic descriptive statistics will be used to characterize the participants including values on the all outcomes. Each person will be classified as a cognitive responder or not based on change on B-CAM. Responder status will be defined as improvement of  $\frac{1}{2}$  SD in B-

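### The protocol defines the linear GEE parameter as effect divided by standard error, which is a test statistic and cannot be read against the 0.5 effect-size benchmark

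*Protocol*

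**What the plan says.** All the relevant text is in the protocol, mainly under Statistical Analysis and Sample.

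- Method: "A linear GEE will be used as the outcomes are continuous although a binary response was used for the primary objective".
- Terms: "The model will include the indicator variable for cohort (CPAP, refuser, or control), time (assessment 1, 2"), followed by age, sex, education, BMI and comorbidity as confounders.
- Power: "As the control cohort will be very much larger than the intervention cohort", the protocol concludes that "statistical comparisons have sufficient power to detect effect sizes of 0.5 or greater". It gives no control number, within-person correlation or numerical power for this statement.
- Interpretation: the next sentence calls the GEE parameter "equivalent to an adjusted effect size (adjusted between cohort effect divided by correlation adjusted standard error").

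Two other places fix the scales. Under Measurement, the B-CAM "yields a score on a continuous metric". The responder rule is in SD units: "Responder status will be defined as improvement of" half an SD on the B-CAM and the C3Q. Nothing else in the protocol redefines the effect size or says that a standard deviation was meant.

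**The concern.** Two consecutive sentences use the term effect size for quantities on different scales. The first sets 0.5 as the detectable effect, which is meaningful only as a fraction of an SD. The second says that what the model estimates is an effect size, and defines it with a standard error in the denominator. A standard error shrinks as people are added; an SD does not. A ratio to the standard error therefore measures how strong the evidence is, not how large the effect is.

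What is at stake is the reported size of the between-cohort effect. The GEE is the only between-cohort analysis described, and the Protocol Summary and Study Objectives word the primary objective as a comparison with people who are not in the intervention. The protocol also says that the findings will inform a larger study. If the definition were followed literally, the number carried forward would depend on how many controls the cohort happened to supply.

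**Working it through.** **1. What the coefficient is.** In a linear GEE the outcome is modelled on its own scale, so a cohort or cohort-by-time coefficient is a difference in means in score points. It is not already a ratio. It equals effect/SD only if the outcome was first divided by that SD.

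**2. What effect/SE is.** Let d be the true difference in change in SD units, m the number of controls and r the within-person correlation, with equal SDs and covariates ignored. For a difference in change between 30 CPAP users and m controls:

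SE/SD = √(2(1−r)) × √(1/30 + 1/m), and effect/SE = d ÷ (SE/SD).

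**3. Inputs.** d = 0.5 is the protocol's benchmark. The value 30 is its target number of adequate users. That is a floor for the CPAP cohort, because the cohort is everyone approached who agreed to enter and recruitment continues until 30 meet the usage threshold. The control number is not stated, so I assume 60 to 470. The upper end is 500 − 30 ("Eligible patients will be identified among the Montreal participants (N=500")); it removes nobody for ineligibility or refusal and would not be reached in practice. The correlation is not stated; I assume 0.5 to 0.8.

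**4. Results for d = 0.5.** There is no protocol figure to reproduce first, because the power statement gives no inputs.

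| Controls m | √(1/30+1/m) | r = 0.5 | r = 0.7 | r = 0.8 |
|---|---|---|---|---|
| 60 | 0.2236 | 2.24 | 2.89 | 3.54 |
| 150 | 0.2000 | 2.50 | 3.23 | 3.95 |
| 470 | 0.1883 | 2.66 | 3.43 | 4.20 |

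End points: 0.5/(1 × 0.2236) = 2.24, and 0.5/(√0.4 × 0.1883) = 0.5/0.1191 = 4.20.

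Conversely, a ratio of 0.5 would correspond to 0.5 × 0.2236 = 0.11 SD at one end and 0.5 × 0.1191 = 0.06 SD at the other.

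**5. Check by simulation.** A linear GEE with exchangeable correlation and a cohort-by-time term was fitted to data with a true effect of 0.5 SD, an arbitrary outcome SD of 4 and r = 0.7, with 60 runs per setting.

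| CPAP vs control | Coefficient (points) | Coefficient/SD | Coefficient/SE |
|---|---|---|---|
| 30 vs 150 | 1.96 | 0.49 | 3.2 |
| 30 vs 300 | 1.85 | 0.46 | 3.2 |
| 300 vs 1500 | 1.98 | 0.49 | 10.2 |
| 300 vs 3000 | 2.01 | 0.50 | 10.7 |

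The raw coefficient is in points. Only the ratio to the SD stays near 0.5 at every sample size.

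**6. Secondary point: which coefficient.** If the listed terms were the whole model, the cohort coefficient would be the between-cohort difference averaged over the two assessments. An effect of 0.5 SD present only at assessment 2 would average to (0 + 0.5)/2 = 0.25 SD. With SE/SD = √((1+r)/2) × √(1/30 + 1/m), effect/SE would then run from 0.25/(√0.9 × 0.2236) = 1.18 (m = 60, r = 0.8) to 0.25/(√0.75 × 0.1883) = 1.53 (m = 470, r = 0.5). This is a different hypothesis from a difference in change, with a different p-value.

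**The case against.** **The wording may mean something on the SD scale.** Standard error could be a slip for standard deviation, or could mean a residual standard error, which is on the SD scale. Either would fit the 0.5 benchmark, but the text says neither. Two problems would also remain. The raw coefficient would equal the ratio only for a standardised outcome, and the phrase about correlation adjustment would leave the SD unnamed. If the SD of change were meant, 0.5 baseline SD would read as 0.5/√(2(1−r)), which is 0.50 at r = 0.5, 0.65 at r = 0.7 and 0.79 at r = 0.8.

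**The sentence only explains.** It does not say that the ratio will be tabulated or judged against 0.5. That stands, so the harm is conditional on the definition being followed. But the protocol fixes the definition itself, so this is not a detail left to an SAP.

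**The list of terms need not be the full model.** It names variables to be included, and the stated reason for GEE is to use both baseline and post-intervention measures, which fits an intended comparison of change. The SAP, not shown, may add the interaction. That stands, which is why this point is secondary and conditional.

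**The illustration is not sized to this trial.** True: 30 is a floor, 470 is out of practical reach, and r is assumed. The scale error follows from the definitions and does not depend on these values.

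A reader might also infer that the power statement is false. The documents do not support that. For 0.5 SD, two-sided 0.05 and the ranges above, power for a difference in change runs from about 61% to 99%. Without the control number and correlation, the statement can be neither confirmed nor refuted.

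**Conclusion.** The definition is wrong as written and should be corrected. A linear GEE coefficient is an adjusted mean difference; divided by its standard error it is a test statistic; neither can be compared with an effect size of 0.5. Under the assumed 30 CPAP users, 60 to 470 controls and r of 0.5 to 0.8, a true 0.5 SD difference in change would read as about 2.2 to 4.2.

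The consequence is modest: it concerns how the size of the between-cohort effect is labelled and read. A reader might infer that the GEE analysis or its p-values are invalid. They are not, because correcting the label alone leaves the fitted model, the p-value and the 7-of-30 rule unchanged. Nor should the point be dismissed because the section ties the binary response to the primary objective. The objective itself is worded as a between-cohort comparison, and the GEE is the only analysis that makes one.

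The cohort-by-time point is different in kind. A reader might infer that the protocol commits to a model without the interaction. The text shows only that the term is not listed. If it was not already intended, adding it would change the between-cohort test and its p-value.

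**What to change.** 1. Delete the parenthesis and the statement that the parameter is equivalent to an effect size.
2. State that the between-cohort result is the adjusted mean difference in outcome units with a 95% CI. Use the standard error only for the interval and the test.
3. If a standardised effect is also reported, divide by one SD named in advance, for example the baseline SD, and say that the 0.5 benchmark is in those units.
4. State that the between-cohort estimate is the cohort-by-time coefficient, and add that term to the list.

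Items 1 to 3 cost a sentence or two and alter only the description of the estimate. Item 4 costs one explicit model term. If the term was not already intended, it changes the between-cohort test, so it should be settled before the data are analysed. None of this needs new data.
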